MedDRA Medical Dictionary for Regulatory Activities

NLP Natural Language Processing

Peg-INF Pegylated interferon
PK pharmacokinetics
PT preferred term

Q1, Q3 first quartile, third quartile

RNA Ribonucleic acid

RR electrocardiographic interval representing the time measurement between the R wave of one

heartbeat and the R wave of the preceding heartbeat

SAE serious adverse event
SAP statistical analysis plan
SD standard deviation
SE Standard error
SOC system organ class

SOF	sofosbuvir
SVR	Sustained Virologic Response
SVRx	sustained virologic response x weeks after cessation of treatment
TEAE	treatment-emergent adverse event
TFLs	tables, figures, and listings
TND	Target not detected
ULN	upper limit of normal
VEL	velpatasvir
WHO	World Health Organization

1. INTRODUCTION

This statistical analysis plan (SAP) describes the statistical analysis methods and data presentations to be used in tables, figures, and listings (TFLs) in the clinical study report (CSR) for Study GS-US-342-5531. This SAP is based on the study protocol dated 03 July 2019 and the electronic case report form (eCRF). The SAP will be finalized before SVR 12 database finalization. Any changes made after the finalization of the SAP will be documented in the CSR.

1.1. Study Objectives

The primary objective of this study is as follows:

- To evaluate the antiviral efficacy of therapy with sofosbuvir/velpatasvir (SOF/VEL) fixed-dose combination (FDC) for 12 weeks as measured by the proportion of subjects with sustained virologic response 12 weeks after cessation of treatment (SVR12)
- To evaluate the safety and tolerability by review of the accumulated safety data

The secondary objectives of this study are as follows:

- To determine the proportion of subjects who attain SVR at 4 and 24 weeks after cessation of treatment (SVR4 and SVR24)
- To evaluate the proportion of subjects with virologic failure
- To evaluate the emergence of viral resistance to SOF and VEL during treatment and after cessation of treatment

1.2. Study Design

This is a multicenter, open-label study evaluating efficacy and safety of SOF/VEL FDC in subjects with chronic HCV infection and compensated cirrhosis.

Subjects may have HCV of any genotype. Based on the HCV genotype (GT) distribution in Japan, it is expected that approximately 70% of subjects will be GT1, and approximately 30% of subjects will be non-GT1. Subjects may be either treatment-naive or treatment-experienced with interferon (IFN)-based treatments.

Approximately 36 subjects will be enrolled to be treated with SOF/VEL FDC for 12 weeks.

The total time to complete all study visits is approximately 40 weeks (42 weeks for those requiring an extension of the Screening period):

- 28 days (4 weeks) screening period [up to 42 days (6 weeks) for extenuating circumstances may be granted]
- 12 weeks study treatment period
- 24 weeks posttreatment period

The schedule of assessment is provided as an appendix to the SAP (Appendix 1).

1.3. Sample Size and Power

A sample size of approximately 36 compensated cirrhotic Japanese subjects in the study will provide > 80% power to demonstrate superiority to a performance threshold of 78%, assuming an expected SVR12 rate of 96% with 12 weeks of SOF/VEL therapy (based on a 2-sided exact 1-sample binomial test of superiority at a significance level of 0.05)

2. TYPE OF PLANNED ANALYSIS

2.1. Data Monitoring Committee

This study does not have a data monitoring committee (DMC).

2.2. Interim Analyses

2.2.1. Posttreatment Week 12 Analysis (Primary Analysis)

The analysis for the primary endpoint SVR12 will be conducted after all subjects complete the posttreatment Week 12 visit or prematurely discontinue from study. All the safety and efficacy data through the posttreatment Week 12 visit will be cleaned, finalized, and included for the analysis.

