8.5. Efficacy Analysis

8.5.1. Primary Analysis

The primary efficacy endpoint for this study will be the proportion of subjects with SVR12, defined as HCV RNA < LLOQ 12 weeks after cessation of treatment. The primary analysis will be performed after all enrolled subjects have been followed through 12 weeks posttreatment or discontinued from study.

In the primary efficacy analysis, the SVR12 rate in FAS will be compared to the efficacy threshold rate of 78% (described in Section 8.7.1) using a two-sided exact one-sample binomial test at significance level of 0.05: ie, the hypothesis for superiority is as follows:

H0: SVR12 rate = 78%,

H1: SVR12 rate \neq 78%

In addition, a point estimate with a two-sided 95% exact confidence interval using the binomial distribution (Clopper-Pearson method) will be constructed for the SVR12 rate.

A success for the primary endpoint will be claimed if the following criterion is met: point estimate of SVR12 is statistically significantly higher than 78% by a two-sided exact one-sample binomial test at significance level 0.05, ie, p-value for above hypothesis testing for superiority is ≤ 0.05 .

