3.4. Multiple Comparisons

No multiplicity adjustment will be made for testing because only one test will be performed.

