3.5. Missing Data and Outliers

3.5.1. Missing Data

In general, missing data will not be imputed unless methods for handling missing data are specified. Exceptions are presented in this document.

For missing last dosing date of study drug, imputation rules are described in Section 3.7.1. The handling of missing or incomplete dates for AE onset is described in Section 7.1.5.2, and for prior and concomitant medications in Section 7.4.

For analyses of categorical HCV RNA data, missing posttreatment HCV RNA data will have the missing data imputed. Missing on-treatment HCV RNA will have missing data imputed up to the time of the last dose (for on-treatment displays). If the study day associated with the last dosing date of the study drug is greater than or equal to the lower bound of a visit window, and the value at the visit is missing, then the value will be imputed. If the study day associated with the last dosing date is less than the lower bound of a visit window, then the on-treatment value at that visit will remain missing.

If an HCV RNA data point is missing and is preceded and followed in time by values that are "< lower limit of quantification (LLOQ) target not detected (TND)," then the missing data point will be set to "< LLOQ TND." If a data point is missing and preceded and followed by values that are "< LLOQ detected," or preceded by "< LLOQ detected" and followed by "< LLOQ TND," or preceded by "< LLOQ TND" and followed by "< LLOQ detected," then the missing value will be set to "< LLOQ detected." In these situations, the data point will be termed a bracketed success; otherwise, the data point will be termed a bracketed failure (ie, \geq LLOQ detected). If a data point is missing and is not bracketed, the missing data point will also be termed a failure (ie, \geq LLOQ detected) except for SVR24, which will be imputed according to SVR12 status. Success for SVR12 who have no further HCV RNA measurements collected will be counted as a success for SVR24 due to the high correlation between these 2 endpoints.

For the analyses of continuous HCV RNA efficacy data, when and only when a missing HCV RNA value is imputed as < LLOQ TND or < LLOQ detected according to the imputation rule described above, the corresponding continuous value will be imputed to LLOQ – 1 IU/mL. No other imputation will be performed for continuous HCV RNA data.

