3.7.2. Analysis Visit Windows

Subject visits might not occur on protocol-specified days. Therefore, for the purpose of analysis, observations will be assigned to analysis windows.

In general, the baseline value will be the last nonmissing value on or prior to the first dose date of study drug.

HCV RNA, vital signs, and safety laboratory data collected up to the last dose date + 3 days are considered to be on-treatment data and HCV RNA, vital signs, and safety laboratory data collected after the last dose date + 3 days are considered posttreatment data. The analysis windows for on-treatment HCV RNA, vital signs and safety laboratory data are provided in Table 1.

Table 1. Analysis Visit Windows for On-treatment HCV RNA, Vital Signs and Safety Laboratory Data

	HCV RNA	and Safety Labo	oratory Data	Vital Signs Data			
Nominal Visit	Nominal FU Day	Lower Limit	Upper Limit	Nominal FU Day	Lower Limit	Upper Limit	
Baseline	1	(none)	1	1	(none)	1	
Week 1	N/A	N/A	N/A	7	2	11	
Week 2	14	2	21	14	12	21	
Week 4	28	22	42	28	22	42	
Week 8	56	43	70	56	43	70	
Week 12	84	71	≥ 85	84	71	≥ 85	

HCV RNA, vital sign, and safety laboratory data collected after the last dose date + 3 days will be assigned to the posttreatment follow-up (FU) visit. Visit windows will be calculated from the last dose date (ie FU Day = collection date minus the last dose date) as shown in Table 2.

Table 2. Analysis Visit Windows for Posttreatment HCV RNA, Vital Signs and Safety Laboratory Data

		HCV RNA		Vital Signs and Safety Laboratory Dat			
Nominal FU ^a Visit	Nominal FU Day	Lower Limit	Upper Limit	Nominal FU Day	Lower Limit	Upper Limit	
FU-4	28	21	69	28	4	30	
FU-12	84	70	146	NA	NA	NA	
FU-24	168	147	210	NA	NA	NA	

a FU-x visit = posttreatment Week-x follow-up visit.

ECG data collected up to the last dose date + 3 days are considered to be on-treatment data. Qualitative assessments of whether the ECG is normal or abnormal will be assessed for on-treatment data based on the visit windows shown in Table 3.

Table 3. Analysis Visit Windows for On-treatment ECG Data

Nominal Visit	Nominal Day	Lower Limit	Upper Limit
Baseline	1	(none)	1
Week 12	84	2	(none)

Note: ECGs are to be collected at screening, baseline, Week 1, and Week 12 or Early Termination. For purposes of analysis, baseline value will be the last available value prior to the first dose of study drug and end of treatment value will be the last available value on or prior to the last dose date + 3 days.

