3.7.3. Selection of Data in the Event of Multiple Records in an Analysis Visit Window

Depending on the statistical analysis method, single values may be required for each analysis window. For example, change from baseline by visit usually requires a single value, whereas a time-to-event analysis would not require 1 value per analysis window.

If multiple valid, nonmissing measurements exist in an analysis window, records will be chosen based on the following rules if a single value is needed:

• For baseline, the last available record on or prior to the date of the first dose of study drug will be selected. If there are multiple records with the same time or no time recorded on the same day, the average (arithmetic mean) will be used for the baseline value. If multiple ECG measurements occur on the same day prior to first dose of any study drug, the average will be used as baseline for continuous data, regardless of the timing of these multiple ECG measurements.

b Days are calculated based on last dose date.

• For postbaseline values:

- The record closest to the nominal day for that visit will be selected except for HCV RNA
 posttreatment follow-up visits, for which the latest record in the analysis window will be
 selected.
- If there are 2 records that are equidistant from the nominal day, the later record will be selected.
- If there is more than 1 record on the selected day, the average will be taken, unless otherwise specified.
- If multiple valid nonmissing categorical observations exist in a window, records will be selected as follows:
 - For baseline, the last available record on or prior to the date of the first dose of study drug will be selected. If there are multiple records with the same time or no time recorded on the same day, the value with the lowest severity will be selected (eg, normal will be selected over abnormal). If multiple ECG measurements occur on the same day prior to the first dose of any study drug, the value with the lowest severity will be selected regardless of the timing of these multiple ECG measurements.
 - For postbaseline visits, follow the same rules described above for postbaseline numeric observations, except that if there are multiple records on the same day, the most conservative value will be selected (eg, abnormal will be selected over normal).

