4.4. Assessment of COVID-19 Impact

This study was ongoing during the novel coronavirus (2019 nCOV [COVID-19]) pandemic which has caused a disruption in the regular visit schedules for this study. Some subjects were unable to attend onsite visits due to shelter in place guidelines, site closures, or other reasons. This section provides how to handle special situations due to COVID-19 in the analysis.

Adverse events due to COVID-19 will be included in AE analyses if applicable.

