6.2.2. Analysis Methods for Secondary Efficacy Endpoints

[figure not shown]
For analyses of SVR4 and SVR24, subjects will be assigned a value at each visit based on the analysis visit windows specified in Section 3.7.2. Missing values will be imputed based on the categorical imputation rules described in Section 3.5.1. The 2-sided 95% exact CI based on Clopper-Pearson method will be provided for the proportion of subjects who attain SVR4 and SVR24 by HCV genotype (GT1 with GT1 broken down as GT1a and GT1b; non-GT1 with non-GT1 broken down as GT2, GT2a/2c and GT2b). The overall category for "HCV RNA < LLOQ" will be split into the following 2 subcategories: "< LLOQ TND" for subjects with target not detected and "< LLOQ detected" for subjects with < LLOQ in tabular displays.

For the virologic failure analysis, a summary table of the number and percentage of subjects with SVR12, virologic failure, and Other will be created. This summary will be performed broken down by HCV genotype (GT1 with GT1 broken down as GT1a and GT1b; non-GT1 with non-GT1 broken down as GT2, GT2a/2c and GT2b). All subjects who achieve SVR12 will be categorized as SVR12. Virologic failure will be descriptively summarized as "on-treatment virologic failure" and relapse (which will be broken down by study drug completed yes/no).

Subjects who do not achieve SVR12 and do not meet criteria for virologic failure will be categorized as "Other." The denominator for relapse will be the number of subjects who had HCV RNA < LLOQ on their last observed on-treatment HCV RNA measurement; otherwise, the denominator will be the number of subjects in the FAS. Virologic outcomes will also be provided by prior HCV treatment experience on FAS overall and by HCV genotype.

A concordance table between SVR12 and SVR24 will be provided by HCV genotype (GT1 with GT1 broken down as GT1a and GT1b; non-GT1 with non-GT1 broken down as GT2, GT2a/2c and GT2b) and overall on FAS who had observed HCV RNA measurements at both posttreatment Week 12 and posttreatment Week 24 visits.

In addition, a summary table of the number and percentage of subjects with HCV RNA < LLOQ and ≥ LLOQ at the posttreatment follow-up visit (observed and imputed, with reasons for imputed) will be provided for each posttreatment follow-up visit overall and by HCV genotype. The 2-sided 95% Clopper-Pearson exact CIs will be presented for the overall proportion of subjects with HCV RNA < LLOQ.

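### Does the Week 12 data scope in SAP 2.2.1 wrongly turn a cured subject with no posttreatment Week 12 sample into a failure?

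*SAP*

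**What the plan says.** SAP 2.2.1 runs the SVR12 analysis once every subject has completed the posttreatment Week 12 visit or left the study early, and sets its data scope: "All the safety and efficacy data through the posttreatment Week 12 visit will be cleaned, finalized, and included for the analysis". Protocol 8.5.1 gives timing only: "The primary analysis will be performed after all enrolled subjects have been followed through 12 weeks posttreatment or discontinued from study".

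SAP 3.5.1 (same rule in Protocol 8.3) imputes a missing categorical HCV RNA value as a success when the values on both sides are below LLOQ. Failing that: "If a data point is missing and is not bracketed, the missing data point will also be termed a failure". The only exception is for SVR24.

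The HCV RNA row for FU-12 in SAP 3.7.2, Table 2, begins with nominal day, lower limit and upper limit: "FU-12 84 70 146 NA NA NA". FU-24 covers Days 147 to 210. SAP 3.7.3 makes posttreatment HCV RNA visits a special case, "for which the latest record in the analysis window will be" used.

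On testing, SAP 3.4 says: "No multiplicity adjustment will be made for testing because only one test will be performed". On attendance, SAP 4.4 says: "Some subjects were unable to attend onsite visits due to shelter in place guidelines, site closures, or other reasons".

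**The concern.** Every sample from Day 70 to Day 146 is itself an FU-12 value, so only a sample from Day 147 on can be the later half of a bracket. If SAP 2.2.1 is a data cut, no such sample is in the primary analysis and bracketing can never rescue a missing FU-12 value there. A subject below LLOQ at FU-4 and again at FU-24 would be a failure at the primary test, yet a success if the same rule were run on the final data.

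The trigger is loose for the same subject. Someone who misses FU-12 but stays on study has neither completed that visit nor discontinued, so neither arm of the SAP wording is met literally, while the protocol wording can be.

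At 36 subjects one reclassification can move the result across the significance boundary, and COVID-19 disrupted visits in this study.

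**Working it through.** **Inputs.** n = 36, threshold 0.78, expected rate 0.96, two-sided exact binomial test at 0.05 (SAP 1.3). Windows from SAP Table 2. The plan does not name the two-sided exact p-value, so both common forms are shown.

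**The plan's own figure.** Write P(X ≥ r | n, p) for the upper binomial tail. At p = 0.78, P(X ≥ 32 | 36) = 0.0775, P(X ≥ 33 | 36) = 0.0289 and P(X ≥ 34 | 36) = 0.0080.

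- Doubled tail: 33/36 gives 2 × 0.0289 = 0.058 and 34/36 gives 2 × 0.0080 = 0.016, so 34 successes are needed. Power is P(X ≥ 34 | 36, 0.96) = 82.7%.
- Minimum likelihood: 32/36 gives p = 0.157 and 33/36 gives p = 0.045, so 33 are needed. Power is P(X ≥ 33 | 36, 0.96) = 94.5%.

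Both agree with the stated power above 80%.

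**Effect if k cured subjects are affected.** Assume the other 36 − k respond at 96%. The documents do not give k. Scored as failures, the k subjects leave P(X ≥ r | 36 − k). Bracketed as successes, they leave P(X ≥ r − k | 36 − k).

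| k | Scoring | Power, 34 needed | Power, 33 needed |
|---|---|---|---|
| 1 | failure | 58.9% | 83.7% |
| 1 | bracketed | 83.7% | 95.0% |
| 2 | failure | 25.0% | 60.3% |
| 2 | bracketed | 84.6% | 95.4% |

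For k = 1 the scoring alone decides the test when the other 35 fall exactly one short:

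- 34 needed: C(35,33) × 0.96^33 × 0.04^2 = 595 × 0.25999 × 0.0016 = 0.2475, or 24.8%.
- 33 needed: C(35,32) × 0.96^32 × 0.04^3 = 6545 × 0.2708 × 0.000064 = 0.1134, or 11.3%.

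**What must coincide for k to be 1.**

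1. No HCV RNA sample for 146 − 70 + 1 = 77 days. The protocol visit is due on Day 84 ± 5 (Days 79 to 89), so a sample up to 146 − 89 = 57 days late still counts as FU-12.
2. A preceding value below LLOQ.
3. The subject stays on study, returns on or after Day 147 and is below LLOQ.
4. That result is in the database when the last subject reaches FU-12. Measured to the last subject's Day 84, the affected subject must have stopped treatment at least 147 − 84 = 63 days earlier, or 168 − 84 = 84 days for a nominal FU-24 visit. The documents give no enrolment period.

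**Direction of error.** Turning successes into failures can only lower the count, so the false-positive rate cannot exceed 0.0080 (34 needed) or 0.0289 (33 needed).

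**What the two readings do.** Take two subjects with the same empty FU-12 window and the same later result below LLOQ, one enrolled early and one late. Under the data-cut reading both are failures. If FU-24 results in hand may bracket, the early one is a success and the late one a failure, because of calendar time alone.

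**The case for a change.** The strongest reply is that conservatism does not excuse an unstated rule. The SAP adopted bracketing, so its reach at the primary analysis should be explicit. Two programmers could follow the text faithfully and reach different SVR12 counts. In an open-label study the choice could be made after FU-24 results are visible.

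Part of this stands. No sentence says whether results from Day 147 on may bracket at the primary analysis, and one subject could matter. But the silence is narrow. SAP 2.2.1 says what is to be cleaned and included, SAP 3.5.1 says how to derive, and the two do not contradict each other. Each reading gives a valid analysis, and the literal one is the stricter.

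An affected subject would also be easy to see. SAP 6.2.2 tabulates observed and imputed results, with reasons, at each posttreatment visit. Someone without SVR12 who meets no virologic failure criterion goes under Other, and an observed FU-24 result below LLOQ still counts for SVR24.

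The remaining parts carry little weight. SAP 3.4 already provides for a single test, so an SVR12 rate re-derived from the final data could only be descriptive. The two trigger wordings can be read as the same milestone, and neither changes any subject's SVR12 status.

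**Conclusion.** No change to the plan is needed. The mechanism is real on one reading of SAP 2.2.1, but that reading gives a uniform, pre-specified missing-as-failure result that errs against the drug. The more generous reading gains something only for early enrollees and scores otherwise identical subjects differently. Choosing between them is a trade-off, and an analyst can follow either defensibly.

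The size is entirely conditional. With one affected cured subject and the rest at 96%, power is 58.9% against 83.7% (34 needed), or 83.7% against 95.0% (33 needed). With no affected subject the difference is zero. The documents give neither an FU-12 missing rate nor an enrolment period, and SAP 4.4 reports missed onsite visits without saying that any FU-12 sample was lost. No overall loss of power can therefore be claimed.

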6.6. Unscheduled Visit

A subject should attend an unscheduled visit if requested by the sponsor or the investigator. The assessments are at the investigator's discretion as clinically indicated, but the investigator should, at a minimum, collect AE and concomitant medication information. At all unscheduled visits initiated for the purpose of confirming virologic failure, a HCV resistance sample must be collected.

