6.2. Secondary Efficacy Endpoints

6.2.1. Definition of Secondary Efficacy Endpoints

Secondary efficacy endpoints include the following:

- The proportion of subjects who attain HCV RNA < LLOQ at 4 and 24 weeks after cessation of treatment (SVR4 and SVR24)
- The proportion of subjects with virologic failure as the following:
 - On-treatment virologic failure
 - HCV RNA ≥ LLOQ after having previously had HCV RNA < LLOQ, while on treatment, confirmed with 2 consecutive values (note, second confirmation value can be posttreatment), or last available on-treatment measurement with no subsequent follow up values (ie, breakthrough)
 - > 1 log₁₀ IL/mL increase in HCV RNA from nadir while on treatment, confirmed with 2 consecutive values (note, second conformation value can be posttreatment), or last available on-treatment measurement with no subsequent follow up values (ie, rebound)
 - \circ HCV RNA persistently \geq LLOQ through 8 weeks of treatment (ie, nonresponse)

— Relapse

O HCV RNA ≥ LLOQ during the posttreatment period having achieved HCV RNA
 < LLOQ at EOT, confirmed with 2 consecutive values or last available posttreatment measurement

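### Does taking SVR12 from the latest HCV RNA up to day 146 conflict with cutting the primary analysis at the posttreatment Week 12 visit?

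*SAP*

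**What the plan says.** **Trigger and content of the analysis.** SAP 2.2.1: "The analysis for the primary endpoint SVR12 will be conducted after all subjects complete the posttreatment Week 12 visit or prematurely discontinue from study". It adds: "All the safety and efficacy data through the posttreatment Week 12 visit will be cleaned, finalized, and included for the analysis". Protocol 8.5.1 words the trigger slightly differently: "The primary analysis will be performed after all enrolled subjects have been followed through 12 weeks posttreatment or discontinued from study".

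**Window.** SAP 3.7.2: "Visit windows will be calculated from the last dose date (ie FU Day = collection date minus the last dose date"). Its Table 2 assigns HCV RNA on days 70-146 to FU-12 and on days 147-210 to FU-24. Protocol 6.3.2 allows ± 5 days around posttreatment Weeks 12 and 24.

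**Choice of record.** SAP 3.7.3 takes the record closest to the nominal day when a window holds several. It makes an exception for HCV RNA "posttreatment follow-up visits, for which the latest record in the analysis window will be" selected.

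**Missing values.** SAP 3.5.1 sets a missing value that lies between two values below LLOQ to below LLOQ: "In these situations, the data point will be termed a bracketed success". A missing FU-12 value that is not bracketed is a failure. Protocol 8.3 has the same rule.

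**Extra samples.** Protocol 6.6: "At all unscheduled visits initiated for the purpose of confirming virologic failure, a HCV resistance sample must be collected". SAP 6.2.1 defines relapse after "LLOQ at EOT, confirmed with 2 consecutive values or last available posttreatment measurement".

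**Later use.** SAP 2.3 plans a final analysis after Week 24. SAP 6.2.2 includes an SVR12/SVR24 concordance table. SAP 3.4 states that there is only one test.

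**The concern.** One rule stops at a visit and the other runs to the end of a much longer window. If a subject gives a second sample after the Week 12 visit but by day 146, the two can disagree:

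- At or above LLOQ on day 84, below LLOQ on a day 98 repeat: failure at the visit cut, success by the latest record.
- Below LLOQ on day 84, at or above LLOQ on day 120: the reverse.

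If the cut is instead read as covering the whole FU-12 window, early enrollees have a complete window when the analysis runs and late enrollees do not. A missed Week 12 sample raises the same question, because only a sample from day 147 on could bracket a value missing over days 70-146. Nor does the SAP say whether the final analysis repeats SVR12 or derives it afresh.

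The stake is the primary test. With 36 subjects it tolerates only two or three failures, so one subject's status can decide it.

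**Working it through.** **1. The plan's power.** Inputs from SAP 1.3 and 6.1.2: N = 36, threshold 78%, expected rate 96%, two-sided exact binomial test at 0.05. The SAP does not name the type of two-sided p-value, so both usual forms are shown.

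| Form of p | p at 33/36 | p at 34/36 | Successes needed | Power at 96% |
|---|---|---|---|---|
| Doubled tail | 0.0578 | 0.0160 | 34 | 0.2516 + 0.3450 + 0.2300 = 0.827 |
| Minimum likelihood | 0.0452 | 0.0144 | 33 | 0.827 + 0.119 = 0.945 (rounded) |

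The summands are the probabilities of 34, 35 and 36 successes; 0.119 is that of 33. Both forms agree with the stated power above 80%.

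**2. The calendar.**
- Week 12 visit: 84 ± 5 = days 79-89.
- Week 24 visit: 168 ± 5 = days 163-173, inside FU-24.
- FU-12 window still open after the visit: 146 - 89 = 57 to 146 - 79 = 67 days.
- Earliest on-schedule Week 24 sample minus the end of FU-12: 163 - 146 = 17 days.

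No HCV RNA is scheduled between day 89 and day 163. Only an unscheduled sample, or a Week 24 sample at least 17 days ahead of its visit window, can replace the Week 12 record.

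**3. The two rules in order.** SAP 2.2.1 says which data are in the analysis. SAP 3.7.3 applies when several valid records exist in a window. Applied in turn to the finalized database, they give one SVR12 status per subject. SAP 1 itself refers to an SVR12 database finalization.

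**4. Which samples could matter.**
- *Confirming a Week 12 value at or above LLOQ.* If the repeat is also at or above LLOQ, both readings give failure. They differ only if the repeat falls below LLOQ off treatment. SAP 6.2.1 does not require a repeat, since the last available measurement can itself establish relapse.
- *Below LLOQ at Week 12, at or above LLOQ by day 146.* Such a subject has no failure to confirm and no visit until day 163. The documents give no occasion for the sample.
- *Missed Week 12 sample.* On the data through that visit the value is unbracketed and counts as failure, which is conservative.

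**5. Size if one such subject exists.** Assume the other 35 respond at 96%. The readings give opposite results when exactly m of the 35 fail, where m is the number of failures tolerated:

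P = C(35, m) × 0.04^m × 0.96^(35-m)

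- m = 2: 0.2475 (power 0.837 if the subject is a success, 0.589 if a failure).
- m = 3: 0.1134 (0.950 and 0.837).
- With the 35 at 94% or 98%: 0.278 or 0.122 (m = 2); 0.195 or 0.027 (m = 3).

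**6. Size over an assumed frequency.** The documents give no rate. Let a share q of would-be successes count as failures under one reading, so that its rate is 0.96(1 - q):

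| Assumed q | Chance of at least one, 1 - (1 - q)^36 | Power loss, 34 needed | Power loss, 33 needed |
|---|---|---|---|
| 0.2% | 7.0% | 1.7 points | 0.8 points |
| 0.5% | 16.5% | 4.4 points | 2.2 points |
| 1% | 30.4% | 9.1 points | 4.7 points |

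This model moves every disputed subject the same way. If both directions were equally likely, both readings would have the same success rate and the power difference would be zero. On the confirmation route, q = 1% means 4.96% of subjects fail at the visit cut and 0.96 points of these are reversed by a repeat: 0.96/4.96 = 19% of those failures. The table therefore leans towards the high side.

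**7. Type I error.** Fixing one subject's outcome and giving the other 35 a rate of 78% does not test the null. The mean rate becomes (35 × 0.78 + 1)/36 = 78.6%, or (35 × 0.78)/36 = 75.8%. Rejection probabilities computed that way do not show a change in the test's error rate.

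**The case for a change.** The best case for a change is that reading the rules in sequence is an inference. Nothing states that FU-12 samples after the Week 12 visit are left out, that the cut waits for day 146, or that SVR12 is frozen. Two programmers could defend different datasets. SAP 4.4 records that COVID-19 disrupted visits, so a missed Week 12 sample is realistic, and the two-week limit for confirming failure in Protocol 3.4.2 covers only the on-treatment phase. The study is open-label, one subject can decide the test, and a sentence in the SAP costs little.

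The silence is real, and so is the sensitivity of a 36-subject test to one result. The rest weakens on inspection:

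- A subject who misses Week 12 but stays in the study is covered by the trigger in Protocol 8.5.1, and SAP 6.4 declares no change from the protocol's efficacy analyses.
- The concordance table is descriptive and limited to subjects observed at both visits. With one planned test, it cannot alter the primary result.
- Fixing SVR12 to the Week 12 sample and barring later samples would drop the bracketing in Protocol 8.3 and ignore a relapse seen after that visit and by day 146. That is less strict than the latest-record rule.
- Waiting until every window closes would delay the primary analysis by 57-67 days in every case, to guard against a sample that no schedule calls for.

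**Conclusion.** No change to the plan follows. As written, it yields a sound SVR12 result: finalize the data through the Week 12 visit, then apply the selection and missing-value rules to what is there. For subjects with on-schedule visits and no extra sample the two readings coincide, and a Week 12 value missing without a bracket counts against the drug. The absent freeze statement is a gap that analysts fill sensibly when they lock the SVR12 database.

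A single disputed subject would give opposite test results with probability 24.8% or 11.3%, depending on the form of the exact p-value, but only if such a subject exists and the other 35 respond at 96%. No document shows one, and the frequencies in the table are assumptions. The stated power above 80% holds under both forms of the test.

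This conclusion rests on the schedule as given, with no HCV RNA planned between day 89 and day 163, and on the Week 12 analysis being the only test.
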